2. STUDY OBJECTIVES

2.1. PRIMARY OBJECTIVE

The primary objective is to evaluate the efficacy of LYR-210 in improving the composite score of 7-day average scores of 4 chronic sinusitis (CS) cardinal symptoms (CS7DA4S) at Week 4.

2.2. KEY SECONDARY OBJECTIVES

The key secondary objectives are:

- To evaluate the efficacy of LYR-210 in improving CS7DA4S score at end of treatment.
- To evaluate the effect of LYR-210 in reducing sinus inflammation as per magnetic resonance imaging (MRI).
- To evaluate the time-to-treatment failure.

2.3. OTHER SECONDARY OBJECTIVES

The other secondary objectives are:

- To evaluate the safety and tolerability of LYR-210.
- To evaluate the time-to-onset of action of LYR-210.
- To evaluate the efficacy of LYR-210 in improving CS7DA4S score and the 7-day average score of each of the 4 CS cardinal symptoms.
- To evaluate the effect of LYR-210 in improving CS disease-specific quality of life as per 22-item sino-nasal outcome test (SNOT-22) questionnaire.

- To evaluate the effect of LYR-210 in reducing sinus inflammation as per MRI.
- To evaluate the effect of LYR-210 in reducing subjects' needs for medical or surgical treatment for CS.
- To evaluate the PK of LYR-210.
- To evaluate the effect of LYR-210 in improving subjects' general quality of life as per 36-item short form health survey version 2 (SF-36v2) questionnaire.
- To evaluate LYR-210 in improving smell function assessed by the University of Pennsylvania Smell Identification Test (UPSIT™).

2.4. EXPLORATORY OBJECTIVES

The exploratory objectives are:

- To evaluate the percentage of subjects experiencing acute exacerbations of CS (AECS).
- To assess effect of LYR-210 in reducing polyp severity within middle meatus in subgroup of CS subjects with nasal polyps (CSwNP).
- To assess efficacy of LYR-210 in improving the below scores in the subgroups of CS subjects without nasal polyps (CSsNP) and CSwNP subjects:
 - CS7DA4S score
 - The 7-day average score of each of 4 CS cardinal symptoms
 - The SNOT-22 total and subdomain scores
 - The SF-36v2 physical health, mental health, and domain scores
- To assess efficacy of LYR-210 in reducing sinus inflammation in CSsNP and CSwNP subjects.
- To assess effect of LYR-210 in improving smell function in CSsNP and CSwNP subjects.
- To assess the safety of subjects, post LYR-210 treatment.
- To assess the durability of efficacy post LYR-210 treatment.

3. STUDY DESIGN

3.1. GENERAL DESCRIPTION

[figure not shown]
This global, multicenter study will be conducted in a randomized, Sham procedure-controlled, parallel-group, subject-blinded fashion in approximately 70 adult CS subjects who have failed previous medical management and have not undergone endoscopic sinus surgery (ESS). The efficacy and safety of LYR-210 (2500 µg) and LYR-210 (7500 µg) versus a Sham procedure only control will be assessed. Additionally, LYR-210 (2500 µg) and LYR-210 (7500 µg) will be compared to evaluate dose related responses.

The study will consist of three stages:

- Screening and washout stage: 2 to 4 weeks.
 - During washout, subjects will receive no active treatment for CS but will be recommended to start daily saline irrigation twice a day.
- Randomized and blinded treatment stage: 24 weeks.
 - Subjects who complete washout and meet all Day 1 eligibility criteria on Day 1 will be stratified according to presence or absence of: 1) nasal allergy (yes vs. no), 2) nasal polyps (yes vs. no).
 - Subjects will be randomized in a 1:1:1 ratio to receive LYR-210 (2500 µg) bilaterally, LYR-210 (7500 µg) bilaterally or Sham procedure bilaterally. Subjects who are assigned to the experimental arms will have the LYR-210 administered bilaterally on Day 1 into the middle meatus and then, removed at Week 24. Subjects who are assigned to the Sham procedure will undergo bilateral mock administration on Day 1 and then, undergo a Sham removal procedure to remain blinded.
 - If spontaneous dislodgement of LYR-210 occurs before Week 24 in subjects who receive either dose of LYR-210, subjects are required to call the study clinic immediately to report the event. If a subject experiences a dislodgement of one of the two LYR-210 depots, the subject will continue the study treatment unless an early treatment discontinuation is recommended by the treating physician or subject requests depot removal from the remaining side of the nose. If depots spontaneously dislodge from both sides of the nose, subject will complete Week 24/End of Treatment (EOT) assessments and subsequently, the post-treatment follow-up stage.
- Blinded post-treatment follow-up stage: 24 weeks.
 - After the Week 24/EOT visit, subjects will undergo post-treatment follow-up for approximately 24 weeks.
 - Except for depot dislodgement, subjects should remain blinded until the final study database is locked.

The overall flow diagram of subject enrolment and follow-up schedule is shown in [Figure 1: Study Design Schematic](#) below:

Figure 1: Study Design Schematic

3.2. SCHEDULE OF ASSESSMENTS

Schedule of assessments can be found in Section 8.1 of the protocol.

3.3. CHANGES TO ANALYSIS FROM PROTOCOL

- The Study Design Schematic was presented in the protocol in Section 4.1. The protocol version 8 did not include the LYR-210 7500 µg treatment arm. An updated version that differs from the protocol is included in the SAP in Section 3.1.
- The endpoint regarding the reduction in subjects' need for specified concomitant medications and medical or surgical treatment for CS will not be analyzed as the data was not collected.
- Section 10.1 of the protocol defines the safety analysis set (SAF) as consisting of all randomized subjects who received the study treatment or treatment attempt on Day 1. For the purposes of the SAP, this has been re-

defined to remove the randomization criteria. It is possible a subject may receive treatment without being formally randomized. Hence the SAF should not contain the randomization restriction.

- Section 10.2 of the protocol states that subject disposition will be summarized for the Intention-to-Treat analysis set (ITT). For the SAP this has been updated to use the All Subjects Consented analysis set (CONS). The ITT for this study includes the condition that subjects will have a post-Day 1 assessment. It is recommended that disposition summaries include all subjects enrolled into the study. Restricting to the ITT will lead to an incomplete summary of subject disposition.
- Section 10.6.1.1 of the protocol describes the one missing value analysis approach as multiple imputation with treatment group as an independent variable in the multiple imputation model. This approach will be conservatively adjusted to apply control-based multiple imputation.
- Section 10.6.1.2 of the protocol describes the model to assess treatment effect across study regions but excludes the stratification variables. The model for the SAP includes the stratification variables. Per ICH E9 all statistical tests/models should be adjusted for any stratification variables.
- Section 10.6.1.2 of the protocol states that subgroup analysis will be performed to assess the treatment effect for the subgroups outlined in Section 7.6 of this SAP and the same model as the region analysis will be used. Due to the small sample size, for the purpose of the SAP one ANCOVA model will be fitted per subgroup to keep the model parsimonious.
- Section 10.6.3 of the protocol states that missing responses to questionnaires at a visit will be imputed using the median of non-missing responses at that visit. For SNOT-22 the literature on this scale indicates that missing responses should be imputed using the mean value of the responses if more than 50% of responses are complete at a visit. The SAP follows this approach and not the protocol defined approach (Hopkins, Gillett, Slack, Lund, & Browne, 2009).
- Section 10.6.4 of the protocol states that, for the generalized estimating equation (GEE) exploratory analysis, if the treatment-by-visit interaction is not significant at the 0.10 level of significance it will be removed from the GEE model. This SAP does not include this criterion, as this is not standard practice. The interaction term will remain in the model even if not significant.

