
To evaluate the effect of LYR-210 in improving CS disease-specific quality of life as per 22-item sino-nasal outcome test (SNOT-22) questionnaire
	
 
- CFBL in total SNOT-22 score and SNOT-22 rhinologic, extra-nasal rhinologic, ear-facial, sleep dysfunction, and psychological subdomain scores at Weeks 2, 4, 8, 12, 16, 20, and 24
 

To evaluate the effect of LYR-210 in reducing sinus inflammation as per magnetic resonance imaging (MRI)
	
 
- CFBL in bilateral Zinreich scores of posterior ethmoid, frontal, sphenoid, maxillary, anterior ethmoid sinus and OMC pairs at Week 24
 
- CFBL in total Zinreich score at Week 24
 

To evaluate the effect of LYR-210 in reducing subjects' needs for medical or surgical treatment for CS
	
 
- Percentage of subjects with use of oral antibiotics for CS through Weeks 4, 8, 12, 16, 20, and 24
 
- Percentage of subjects with use of oral corticosteroid for CS through Weeks 4, 8, 12, 16, 20, and 24
 
- Percentage of subjects with use of intranasal corticosteroid sprays for CS through Weeks 4, 8, 12, 16, 20, and 24
 
- Percentage of subjects being recommended by treating physician for ESS through Weeks 4, 8, 12, 16, 20, and 24
 

To evaluate the pharmacokinetics of LYR-210
	
 
- Plasma MF concentrations at [REDACTED] 4, 12, 24
 
 
[REDACTED]

To evaluate the effect of LYR-210 in improving subjects' general quality of life as per 36-item short form health survey version 2 (SF-36v2) questionnaire
	
 
- CFBL in SF-36v2 physical health, mental health, and domain scores at Week 24
 

To evaluate LYR-210 in improving smell function assessed by the University of Pennsylvania Smell Identification Test (UPSIT™)
	
 
- CFBL in UPSIT score at Week 24
 

Exploratory
	

To evaluate the percentage of subjects experiencing acute exacerbations of CS (AECS)
	
 
- Percentage of subjects experiencing AECS through Weeks 4, 8, 12, 16, 20, and 24
 
 
AECS is defined as a sudden worsening of symptoms in a subject resulting in the treating physician reporting an escalation of treatment.

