12. MEDICATIONS

Medications other than CS medical treatment history (see Section 10) will be coded World Health Organization Drug Dictionary (WHO-DD) version March 2020 or later. No Anatomical Therapeutic Class (ATC) coding will be performed for this study.

See APPENDIX 2 for handling of partial dates for medications. In the case where it is not possible to define a medication as prior, concomitant, or post-treatment, the medication will be classified by the worst case; i.e. concomitant.

- ‘Prior’ medications are medications which started and stopped prior to the bilateral insertion/Sham procedure or treatment attempt.
- ‘Concomitant’ medications are medications which:
 - started prior to the bilateral insertion/Sham procedure/treatment attempt AND were ongoing or ended after the bilateral insertion/Sham procedure/treatment attempt;
 - started on the day of the bilateral insertion/Sham procedure/treatment attempt;
 - started after the bilateral insertion/Sham procedure/treatment attempt but before or on the removal/Sham removal + 28 days.
- ‘Post-treatment’ medications are medications which started after the bilateral removal/Sham procedure + 28 days.

Prior, Concomitant and Post Medications will be listed by WHO drug name concatenated with base name for the SAF analysis set.

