15.2.1.3. Time-to-Treatment Failure

Time-to-treatment failure, in days, will be derived as:

$$\text{Time (days)} = \text{date of treatment failure} - \text{treatment start date} + 1$$

Where treatment failure is defined as:

- after subject enrollment, the subject being recommended by treating physician for oral corticosteroid or ESS due to worsening of CS symptoms as collected on the Follow-up eCRF

OR

- the subject complaining of persistent CS symptoms, i.e., has an average CS7DA4S score over the preceding 30 days greater than or equal to the baseline CS7DA4S score as defined by ██████████ Biostatistics.
 - The earliest timepoint at which to calculate this score is Day 31. For each day post-Day 30, the average CS7DA4S over the preceding 30 days will be derived and compared to the baseline CS7DA4S score
 - The average CS7DA4S for at least 21 of the preceding 30 days should be available for this derivation.

Subjects without the event will be censored at their follow-up period. That is, should a subject reach Week 24 without having met the criteria for the time-to-treatment failure, the subject will be censored at the date of the Week 24 visit; should a subject discontinue early from the study before Week 24 without having met the criteria for the time-to-treatment failure, the subject will be censored at the date of discontinuation from study.

Time-to-treatment failure will be derived at different timepoints: Weeks 2 (15 days), 4 (29 days), 8 (57 days), 12 (85 days), 16 (113 days), 20 (141 days) and 24 (169 days). These timepoints are independent of the scheduled visits.

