15.2.4.3. Analysis of Time-to-Treatment Failure

The number and percentage of subjects with and without treatment failure will be presented based on the ITT analysis set. For subjects without treatment failure, the censoring reason will be summarized. Time-to-treatment failure (days) will be analyzed for the ITT analysis set using a Cox proportional hazards model with fixed effects for baseline CS7DA4S score, treatment group and the stratification variables (nasal allergy and nasal polyps). The Hazard ratio of each LYR-210 treatment group vs. the Sham treatment group, its 90% CI and p-values will be presented.

Additionally, Kaplan-Meier results will be displayed for the 25%, 50% and 75% quartiles, along with Kaplan-Meier estimates of probability of treatment failure at different timepoints: Weeks 2, 4, 8, 12, 16, 20 and 24. These timepoints are independent of the scheduled visits. Kaplan-Meier plots of time-to-treatment failure will be produced for each treatment group.

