APPENDIX 1. PROGRAMMING CONVENTIONS FOR OUTPUTS

PAPER SIZE, ORIENTATION AND MARGINS

The size of paper will be Letter, and the page orientation will be landscape. Margins will provide 1 inch (2.54 cm) of white space all around the page.

DATES AND TIMES

Depending on data available, dates and times will take the form DDMMYYYY HH:MM.

SPELLING FORMAT

United States English.

PRESENTATION OF TREATMENT GROUPS

For outputs, treatment groups will be represented as follows and in the given order:

- LYR-210 2500µg
- LYR-210 7500µg
- Sham

PRESENTATION OF VISITS

For tables and figures, visits will be represented as follows and in that order:

Long Name (default)	Short Name
Screening	Scr
Baseline	BL
Week 2	WK 2
Week 4	WK 4
Week 8	WK 8
Week 12	WK 12
Week 16	WK 16
Week 20	WK 20
Week 24	WK 24

Long Name (default)	Short Name
Week 28	WK 28
Week 32	WK 32
Week 36	WK 36
Week 40	WK 40
Week 44	WK 44
Week 48	WK 48

For Listings the visit will be presented as derived in Section 6.6.

LISTINGS

All listings will be ordered by the following (unless otherwise indicated in the template):

- Randomized treatment group (or treatment received if it's a safety output) in order of LYR-210 2500 µg, LYR-210 7500 µg and Sham procedure.
 - For listings where non-randomized subjects are included, these will appear in a category after the randomized treatment groups labeled “Randomized, Not Treated” and “Screen Failure”.
- Subject ID
- Parameter (where applicable)
- Date (where applicable)

GENERAL CONVENTIONS

- Decimal precision:
 - If the original data has N decimal places, then the summary statistics should have the following decimal places:
 - Minimum and maximum: N
 - Mean and median: N + 1
 - SD: N + 2
 - Percentages will be presented to 1 decimal place
 - Zero count will not have percentage reported
 - Odd ratios will be presented to 2 decimal places
 - Ordering of footnotes:
-

Statistical Analysis Plan

- Abbreviations
- Definitions
- Formulae
- P-value significance footnote
- Symbols. They will appear in the same order as they are defined in the table or listing, from left to right.
- Specific notes
- Common notes from table to table should appear in the same order.

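### SAP 3.3 drops the treatment-need endpoints as uncollected, but SAP 15.2.1.3 uses Follow-up eCRF recommendations for oral corticosteroid or ESS, which the SAP text reports only inside a composite

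*SAP*

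**What the plan says.** Protocol Section 3 gives one secondary objective on subjects' need for CS treatment four endpoints, each cumulative through Weeks 4, 8, 12, 16, 20 and 24. Three are percentages of subjects using, for CS, oral antibiotics, oral corticosteroid or nasal steroid sprays. The fourth is "Percentage of subjects being recommended by treating physician for ESS through Weeks 4, 8, 12, 16, 20, and 24".

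SAP 2.3 keeps the objective: "To evaluate the effect of LYR-210 in reducing subjects' needs for medical or surgical treatment for CS". SAP 3.3 then removes the analysis, saying that the endpoint on specified medicines and "medical or surgical treatment for CS will not be analyzed as the data was not collected". It gives this one reason for the whole group and does not go item by item.

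SAP 15.2.1.3 defines treatment failure by either of two criteria. The first is "the subject being recommended by treating physician for oral corticosteroid or ESS due to worsening of CS symptoms as collected on the Follow-up eCRF". The second is a 30-day average CS7DA4S at or above the baseline score, for which "The earliest timepoint at which to calculate this score is Day 31".

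SAP 15.2.4.3 plans counts with and without failure, a Cox model, and Kaplan-Meier results with estimates at Weeks 2, 4, 8, 12, 16, 20 and 24. On reasons, it says only: "For subjects without treatment failure, the censoring reason will be summarized".

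**The concern.** The reason given for dropping a set of protocol secondary endpoints does not fit the rest of the SAP. At least one dropped endpoint, physician recommendation for ESS, is the same kind of event that the SAP says is recorded and uses for a key secondary endpoint. A reader of SAP 3.3 cannot tell which items were really missing.

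The second issue is interpretation. Protocol 6.3 says that after randomization the site staff, including the Investigator, know whether a subject had LYR-210 or sham, and Protocol 6.4.4 gives the Investigator the rescue decision. Subjects are meant to stay blinded, apart from cases of depot dislodgement. So the recommendation criterion comes from unblinded judgment and the score criterion from blinded self-report. If only the composite is shown, a difference between arms cannot be traced to one or the other.

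**Working it through.** **Step 1. Compare each dropped endpoint with SAP 15.2.1.3.**

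| Dropped endpoint | What SAP 15.2.1.3 says is on the Follow-up eCRF | Result |
|---|---|---|
| ESS recommended | Recommendation for oral corticosteroid or ESS, for worsening symptoms | Conflict, unless the form holds one combined item |
| Oral corticosteroid use | The same item, but a recommendation and not use | Conflict by proxy only |
| Oral antibiotic use | Nothing | Not contradicted |
| Nasal steroid spray use | Nothing | Not contradicted |

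The dropped set is 4 measures × 6 time points = 24 percentages per arm. ESS recommendation accounts for 6, oral corticosteroid for 6, and the other two for 12.

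**Step 2. Find when each failure criterion can act.** The score criterion starts at Day 31. The SAP's time points are Days 15, 29, 57, 85, 113, 141 and 169.

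- Days 15 and 29 (Weeks 2 and 4) fall before Day 31, so any failure counted there is a recommendation.
- Days 57 to 169 (Weeks 8, 12, 16, 20 and 24) fall after it, so the two criteria are mixed: 5 of 7 time points.

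Because the analysis is time to first event, a recommendation made after a score failure does not enter it.

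**Step 3. Look for another by-arm output.**

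- The acute exacerbation endpoint (SAP 15.3.1.1, 15.3.3) is compared between arms at Weeks 4 to 24. It covers any escalation of treatment and does not identify oral corticosteroid or ESS.
- SAP 9 gives reasons for discontinuation by arm, which shows only subjects who stopped.
- SAP 12 lists medicines and plans no table of them.

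**Step 4. Precision of the missing table.** The per-arm number comes from SAP 7.1, whose stated 73% power can be reproduced. With a difference of 1.7, SD 2.4 and 21 per arm, the noncentrality is 1.7 / (2.4 × √(2/21)) = 2.295. The noncentral t distribution with 40 df gives 73.0% at one-sided 0.05, for one dose against sham. That figure serves here only to fix n = 21.

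The documents give no event rates, so I assume a common rate p in both arms. The 90% half-width for a difference is 1.645 × √(2p(1−p)/21):

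- p = 0.10: 15.2 percentage points
- p = 0.20: 20.3 percentage points
- p = 0.30: 23.3 percentage points

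**The case against.** The strongest reply is that the conflict depends on a form that is not in the documents. SAP 15.2.1.3 names oral corticosteroid or ESS together. If that is one field, ESS recommendation alone was never captured, and SAP 3.3 is literally right about it. SAP 15.2.1.3 also refers to a date of treatment failure without saying that a recommendation date is recorded. This stands, and the conclusion is conditional on it. SAP 3.3 would still need to say so, because its text gives no hint that a combined item exists.

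The absence of a split by criterion also cannot be confirmed. SAP 8 leaves the format and content of tables to shells supplied with the SAP, and those are not available here. The point therefore rests on the SAP text alone.

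The composite follows Protocol 10.6.2.3, which asks for no split. Ignoring later events is normal in a time-to-first-event analysis, and SAP 7.8 describes the study as exploratory with nominal p-values. All of this is true. It limits the weight of the point but does not repair the stated reason for the drop.

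A reader might infer that all four data items were in fact collected. Protocol 6.4 says all medicines taken are recorded, Protocol 6.4.4 requires the rationale for oral corticosteroid use, and SAP 5.7 searches concomitant medications for mometasone. But the endpoints concern use for CS, and no indication field is shown. SAP 12 adds: "No Anatomical Therapeutic Class (ATC) coding will be performed for this study". The documents do not show that SAP 3.3 is wrong on antibiotics or sprays.

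A reader might also infer that the objective gets no by-arm information at all. That goes too far. The Kaplan-Meier estimates at Weeks 2 and 4 reflect recommendations only, and the acute exacerbation comparison gives a broader measure of escalation.

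**Conclusion.** The point holds in limited form and should be corrected. The reason in SAP 3.3 conflicts with SAP 15.2.1.3 for one of four endpoints, conflicts by proxy for a second, and is not contradicted by that section for the other two. In the SAP text, treatment failure is composite only, with recommendation and score failures mixed at 5 of 7 time points.

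This rests on three assumptions: that the eCRF separates ESS from oral corticosteroid, that the table shells do not already show failures by criterion, and that the treating physician who recommends is among the unblinded site staff. If the first fails, the ESS conflict becomes a need for clearer wording. If the second fails, the treatment-failure table needs no change.

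The documents do not support reading the drop as concealed, since SAP 3.3 discloses it. Nor do they show that recommendations were in fact biased; the plan simply gives no way to look. The primary endpoint is unaffected.

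**What to change.** 1. Reword SAP 3.3 to state, item by item, which data were not collected, and reconcile it with SAP 15.2.1.3.
2. Add one descriptive table by arm, through Weeks 4, 8, 12, 16, 20 and 24, with the number and percentage of subjects with a Follow-up eCRF recommendation for ESS and for oral corticosteroid. Use one combined row if the form does not separate them. Include recommendations made after a score failure where they are recorded. Footnote that the item is limited to worsening CS symptoms and that recommendation is not use.
3. In the treatment-failure table, add the number of subjects failing first by each criterion, unless the shells already do so.

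The cost is a wording change, one small table and one block of rows, from data already needed for treatment failure. The table will be imprecise and should carry no test. Tables of medication use are not part of this fix.

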#### **10.6.1.2 Assessment of Treatment Effect Across Study Regions, Across Nasal Allergy Groups and Across Polyp Groups**

To assess consistency of treatment difference across study region, descriptive statistics of the primary endpoint will be presented by treatment group within each region. An exploratory analysis of covariance on the primary endpoint, with independent variables of treatment group, region, baseline CS7DA4S score, and treatment by region interaction, will be carried out on the ITT analysis set with available data.

Similar analyses will be presented to assess consistency of treatment effect across nasal allergy groups (yes/no) and polyp groups (yes/no). Assessment of consistency across subgroups such as baseline CS7DA4S (below median, at or above median), sex and age (below median, at or above median) will be conducted as well. All subgroups to be assessed for treatment effect consistency on the primary endpoint will be detailed in the statistical analysis plan. These analyses will be carried out on the ITT analysis set with available data.

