15.1.5.2. Assessment of Treatment Effect Across Subgroups Described in Section 7.6

To assess the consistency of treatment difference across subgroups, descriptive statistics of the primary endpoint will be presented by treatment group within each subgroup. An exploratory analysis of covariance on the CFBL of CS7DA4S score at Week 4 will be carried out on the ITT analysis set for subjects with available data. The ANCOVA model will include the baseline CS7DA4S score as a covariate, the stratification variables, and treatment group as a fixed effect and will be repeated for each subgroup of interest.

If data is too sparse for at least one treatment group in at least one subgroup (i.e., less than 5 ITT subjects for at least one treatment group in at least one subgroup), only descriptive statistics by subgroup will be provided.

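### The within-level subgroup ANCOVAs give no estimate of the difference in effect between levels, and the parsimony reason for dropping the interaction model does not hold for the pair of fits

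*SAP*

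**What the plan says.** Protocol 10.6.1.2 assesses consistency across regions with an ANCOVA "with independent variables of treatment group, region, baseline CS7DA4S score, and treatment by region interaction". It plans similar analyses for nasal allergy and nasal polyps. For baseline score, sex and age it says consistency will also be assessed, names no model, and leaves the list of subgroups to the SAP.

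SAP 3.3 describes the protocol more broadly, saying that for the SAP 7.6 subgroups "the same model as the region analysis will be used". It then changes this: "one ANCOVA model will be fitted per subgroup to keep the model parsimonious", giving small sample size as the reason.

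SAP 15.1.5.2 keeps the aim of assessing consistency of the treatment difference. Its model has baseline CS7DA4S as a covariate, "the stratification variables, and treatment group as a fixed effect and will be repeated for each subgroup of interest". There is no subgroup term and no interaction. Two other sections confirm that the fits are made within levels: SAP 7.6 switches inference off for a single sparse subgroup, and SAP 15.3.3 drops the polyp term in the analyses with and without polyps.

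Region is treated differently. SAP 15.1.5.1 keeps a model with region and treatment-by-region, with the stratification variables, and looks at the interaction at the 0.15 level.

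**The concern.** Consistency is a question about the difference between two treatment effects. Two separate fits give two effects, each with its own interval, and the SAP does not specify how to compare them. If one level shows a nominally significant effect and the other does not, the display suggests a difference in effect. At this sample size that pattern is common even when the effects are identical.

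The stated reason is also open to question. A small sample usually argues for sharing covariate slopes and residual variance across levels. Separate fits share neither, while region, with the same sample, keeps the shared model.

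What is at stake is the interpretation of exploratory subgroup results on the primary endpoint. SAP 15.2.4.1 repeats the same subgroup analysis for the CS7DA4S total score at the other weeks, including Week 24. No primary or key secondary test depends on it.

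**Working it through.** **Inputs.** From SAP 7.1: difference 3.00 − 1.30 = 1.70, SD 2.4, 21 evaluable subjects per arm (63 in all), one-sided 0.05, stated power 73%. From SAP 15.1.5.1 and 15.1.5.2 and protocol 10.6.1.2: the model terms. The documents do not give level sizes, so 10/11 per arm (roughly a median split) and 6/15 per arm (an uneven split) are assumptions.

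**Plan's own figure.** SE = 2.4 × √(2/21) = 0.741, noncentrality 1.70/0.741 = 2.30. The noncentral t gives 73.0% (40 df) or 73.4% (60 df) for one dose against sham. The stated 73% is reproduced, so these inputs are used below.

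**Parameter count per two-level factor.**
- SAP fit within one level: intercept 1 + treatment 2 + baseline 1 + strata 2 = 6. Two levels: 12 mean parameters, 2 variances, 63 − 12 = 51 residual df split between two fits.
- Region-type model of SAP 15.1.5.1 applied to the factor: 1 + 2 + 1 + 2 + subgroup 1 + interaction 2 = 9, 1 variance, 54 residual df.
- Protocol model as written, without strata: 1 + 2 + 1 + 1 + 2 = 7, 1 variance, 56 residual df.
- Allergy or polyps: the factor is constant within its own level, so 5 parameters are estimable per fit and 10 in all. The region-type model has 8, because the factor enters once (55 residual df).

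For the other factors, the three extra parameters (12 − 9) are level-specific slopes for baseline, allergy and polyps.

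**How often the levels disagree when the true effect is 1.70 in both.** Chance = pA(1 − pB) + pB(1 − pA), with pA and pB the power in each level.
- 10/11 per arm (24 and 27 df): powers 0.458 and 0.490. 0.458 × 0.510 + 0.490 × 0.542 = 0.50.
- 6/15 per arm (allergy or polyps, 13 and 40 df): powers 0.315 and 0.603. 0.315 × 0.397 + 0.603 × 0.685 = 0.54.
- Same splits with one pooled variance on 55 df, by simulation: 49% and 53%. Pooling does not remove the disagreement, which comes from dividing the sample.

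**Per-level precision (90% CI half-width, 5-parameter fits).**
- 6 per arm: SE 2.4 × √(2/6) = 1.386. Separate 1.771 × 1.386 = 2.45; pooled 1.673 × 1.386 = 2.32, about 5% narrower.
- 10 per arm: SE 1.073. Separate 1.708 × 1.073 = 1.83; pooled 1.673 × 1.073 = 1.80, about 2% narrower.

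**Precision of the missing contrast.**
- 10/11: SE = 2.4 × √(2/10 + 2/11) = 1.483; half-width 1.674 × 1.483 = 2.48.
- 6/15: SE = 2.4 × √(2/6 + 2/15) = 1.640; half-width 1.673 × 1.640 = 2.74.
- Power for an effect of 1.70 in one level and 0 in the other, even split, one dose: about 20% at two-sided 0.05 and 39% at 0.15. The 2-df test over both doses gives 19% and 38%.

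**The case against.** The other side has several good points.

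- **A single fit is smaller.** It has 6 mean parameters against 7 or 9, which is probably what the SAP means. This stands for one fit, but that fit uses only part of the data and the factor needs two.
- **The contrast is unplanned, not unavailable.** The levels hold different subjects, so (d1 − d2)/√(SE1² + SE2²) follows from the estimates and SEs that SAP 15.1.3 provides. A reader might infer that consistency cannot be tested at all from these fits. That goes too far; the SAP simply does not plan the comparison.
- **No significance rule is written.** A reader might infer that consistency will be judged by significance in one level and not in the other. Neither document says so, and LS mean differences with 90% CIs are reported too. The 50% to 54% figure is a warning against that way of reading the results, not a description of a planned rule.
- **The protocol commitment is narrower than SAP 3.3 suggests.** A reader might infer that the protocol fixed an interaction model with strata for every subgroup. It extends the region approach explicitly only to allergy and polyps, its model has no strata, and the Zinreich subgroup is not in its list.
- **The gain is limited.** Per-level intervals narrow by 2% to 5%, the interaction has little power, and separate fits avoid assuming common slopes and variance. All of this stands.
- **The constant stratum is a wording slip.** A one-level factor drops out without altering the treatment contrast. SAP 15.3.3 drops polyps for the polyp subgroups; nothing does so for allergy.

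The change is also disclosed, and SAP 7.6 says that the study was not designed for high power within subgroups.

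**Conclusion.** The point holds in a limited form. SAP 15.1.5.2 states a between-level question and plans only within-level answers. The parsimony argument fails for the analysis as a whole: 12 mean parameters and 2 variances against 9 and 1 (7 and 1 as the protocol wrote it), or 10 against 8 mean parameters for allergy or polyps. With equal true effects the two levels would differ in significance in about 50% to 54% of trials for a given dose. This assumes difference 1.7, SD 2.4, all 63 subjects evaluable, and level sizes of 10/11 or 6/15 per arm.

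A reader might infer that a pooled model would cure that disagreement. It would not: the figure stays at about 49% to 53%. The reason to change is the contrast itself. Its 90% CI, about 2.5 to 2.7 points either side against an assumed effect of 1.7, shows how little can be concluded about consistency. Two separate results do not show that. Severity is minor.

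**What to change.** In SAP 15.1.5.2, apply the SAP 15.1.5.1 model form to each two-level factor: baseline CS7DA4S, nasal allergy, nasal polyps, treatment, subgroup and treatment-by-subgroup. Enter the factor once when it is itself a stratification variable, which also removes the constant-term problem. For each dose, report the LS mean difference from sham in each level and the difference between levels, all with 90% CIs and whatever the interaction p-value. Keep the descriptive-only rule for fewer than 5 subjects per arm. Correct the parsimony rationale in SAP 3.3.

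The cost is one model statement per factor in place of two, with no new data. The model assumes common covariate slopes and a common residual variance across levels, which the SAP already accepts for region. If the separate fits are kept, the SAP should call them descriptive, drop the parsimony argument, and add the between-level difference with its 90% CI from the two estimates and their SEs.
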